5.1.1 Screening Period

The screening period will be up to 35 days, and begins when the participant signs the main informed consent form (ICF). During the screening period, participants will submit a fresh biopsy which will be evaluated for adequate and evaluable tumor tissue by the central laboratory. Only those participants who have met tissue quality thresholds and have evaluable CD8 and HLA-E can be assigned for treatment in PD cohorts. Please refer to the laboratory manual for additional details. Participants will be allocated in the PD cohorts according to CD8 and HLA-E expression. Participants must have a lesion that can be biopsied at an acceptable clinical risk as judged by the investigator in order to be eligible for the study; see [Table 2-1](#). Participants will be enrolled using an Interactive Response Technology (IRT). The screening assessments are shown in Table 2-1. If a participant exceeds the 35-day screening period due to a study-related procedure (eg, scheduling of a tumor biopsy or waiting for a study-related laboratory value), the participant must be re-consented, but does not require a new participant identification number. In this situation, safety laboratory tests should be repeated and the Bristol Myers Squibb (BMS) Medical Monitor or designee should be notified. Any additional procedures and tests should only be repeated if needed to maintain participant safety and confirm eligibility after discussion with the BMS Medical Monitor or designee.

5.1.2 Treatment Period

The dosing regimen of BMS-986315 is Q4W. Refer to [Section 5.1 Overall Design](#). All participants will be treated for up to 104 weeks. The treatment period will consist of up to 26 treatment cycles (each cycle is 4 weeks in length). Continuous safety evaluation and tumor assessment (every 8 weeks [Q8W]) will guide the decision to treat a participant with additional cycles of study therapy if the participant has confirmed clinical benefit (up to a maximum of 104 weeks) for all study parts.

Study visits in Part 1A (BMS-986315 Monotherapy Dose Escalation) will be performed every 2 weeks for the first 8 weeks following the first dose of study treatment. BMS-986315 will be administered every 4 weeks (Q4W) and will be infused over approximately 60 minutes for the first 2 cycles and then approximately 30 minutes for cycles 3 and beyond. BMS-986315 will require a 4 hour observation period following the completion of the infusion for the first dose in the escalation cohort and 60 minutes observation for the second dose for each participant. For the pharmacodynamic cohorts, the observation period is 60 minutes for the first 2 doses. See [Table 2-](#)

2. Please refer to the pharmacy manual for dose-specific infusion times and administration details for BMS-986315.

In Part 1B (BMS-986315 in Combination with Nivolumab Dose Escalation) nivolumab will be administered Q4W and will be infused over 30 minutes. Nivolumab will be given first, followed by a 30-minute observation period. After that, BMS-986315 will be infused over approximately 60 minutes for the first 2 cycles and then over approximately 30 minutes for cycles 3 and beyond. BMS-986315 infusions will require a 60-minute observation period following the completion of the infusion for the first 2 doses for each participant. Please refer to the pharmacy manual for dose-specific infusion times and administration details for nivolumab and BMS-986315.

In Part 1C (BMS-986315 in Combination with Cetuximab Dose Escalation) cetuximab will be administered Q2W and will be infused over 150 minutes for the first dose, and 120 minutes for subsequent doses. Cetuximab will be given first, followed by a 60-minute observation period. After that, BMS-986315 will be infused over approximately 60 minutes for the first 2 cycles and then over approximately 30 minutes for cycles 3 and beyond. BMS-986315 infusions will require a 60-minute observation period following the completion of the infusion for the first 2 doses for each participant. Please refer to the pharmacy manual for dose specific infusion times and administration details for cetuximab and BMS-986315.

All eligible participants will be initially assigned to Part 1A (dose escalation of BMS-986315 monotherapy). Treatment in Part 1B and Part 1C will be initiated in a staggered manner relative to the dose escalation of BMS-986315 (Part 1A). Specifically, Part 1B and Part 1C can be initiated when at least 2 dose levels (the current and 1 one higher) in Part 1A have cleared the DLT period in accordance with dose escalation rules, after which dose escalation in Part 1A, Part 1B, and Part 1C will proceed in parallel. At no point will the dose of BMS-986315 administered in combination with nivolumab in Part 1B or cetuximab in Part 1C exceed the highest safe dose in ongoing monotherapy dose escalation in Part 1A, or the highest dose determined to be tolerated in Part 1A.

The monotherapy and combination dose escalation cohorts will be kept separated by 2 dose levels (the current and 1 higher) until dose escalation in monotherapy is completed. Initially, 3 participants will be enrolled at the start of each cohort via staggered dosing (see Sentinel Participant below). Additional information on DLTs can be found in [Section 5.1.3](#).

Participants may be enrolled to backfill dose escalation cohorts in Part 1A, Part 1B, or Part 1C. Any available PD, PK, and clinical data obtained from backfill participants will be utilized among the totality of data considered for dose selection. Backfill will not result in treatment of participants exceeding maximum participant numbers planned for the study. Enrollment of backfill participants requires prior consultation with the medical monitor.

Sentinel Participant:

During the dose escalation phase in Parts 1A, 1B, and 1C, a staggered dosing (sentinel participant) approach, will be used. In Part 1A the first participant to be dosed at C1D1 of the first dose level will be observed for 5 days, before additional participants (ie, Participant 2 onward in that cohort) receive study treatments in the same dose level. In Parts 1B and 1C, the first participant to be dosed

at C1D1 of each dose level will be observed for 5 days, before additional participants (ie, Participant 2 onward in each cohort) receive study treatments in the same dose level.

5.1.2.1 BMS-986315 Monotherapy Dose Escalation Design (Part 1A)

Approximately 36 participants are expected to be treated during the BMS-986315 Monotherapy Dose Escalation (Part 1A) of the study guided by TITE-BOIN design ([Figure 5.1.2.1-1](#), TITE BOIN [Appendix 8](#)) for the primary objective. Additionally, up to approximately 40 participants are expected to be treated in the SCCHN PD cohort in monotherapy (in order to have 30 evaluable).

[figure not shown]
In dose escalation, each participant will be administered IV doses of BMS-986315 in planned dose levels of 80 mg followed by 200 mg, 600 mg, 1200 mg, and 2400 mg Q4W once per cycle, for up to 26 cycles (104 weeks) of study therapy, unless criteria for study drug discontinuation are met earlier (see [Section 8](#)).

Prior to declaring the MTD, and in consultation with investigators, the Sponsor has the option to investigate dose levels intermediate to those defined in the protocol. Planned dose levels may be modified based upon the DLT data in the evaluated doses and clinical evaluation of all available safety and PK/pharmacodynamic data. Once the tolerability (during the DLT evaluation) of a dose level has been established, additional participants may be added at that dose level to better characterize the safety, PK, and pharmacodynamic profiles.

The BMS-986315 Monotherapy Dose Escalation (Part 1A) phase of the study will evaluate the safety and tolerability of BMS-986315, based on DLTs, guided by the TITE-BOIN design. During the monotherapy dose escalation phase, approximately 3 participants will be treated at each dose level, allowing at least 2 participants for a decision at the lower dose levels. In order to allow for any unforeseen discontinuations (such as disease progression) before the 4-week DLT period (28 days) is completed, an extra participant may be enrolled in each dose escalation cohort after the 2 initial dose levels. Therefore, there may be a total of 4 participants (3 + 1) at the start of a cohort. Cohort tolerability assessment and subsequent dose recommendation will occur when at least 2 out of 3 or 3 out of 4 participants within a cohort have completed the 4-week (28 day) DLT period or have been followed sufficiently based on the TITE-BOIN design to make an escalation decision. Any toxicities that occur beyond the DLT period will be considered in making dose level decisions and/or dose level modifications. Additional information on DLTs can be found in [Section 5.1.3](#).

If the potential DLT occurring in the third evaluable participant regarding any specific dose level does not influence the dose recommendation by TITE-BOIN, the next dose level may proceed without waiting for the third participant to complete the corresponding DLT-observation period, after discussion and agreement between the Sponsor and investigators. Continuous reassessment of dose recommendation, by TITE-BOIN in the BMS-986315 Monotherapy Escalation (Part 1A) will be carried out for each dose level. Planned dose levels for dose escalation are provided in [Section 5.1 Overall Design](#).

Figure 5.1.2.1-1: Flowchart Using the TITE-BOIN Design

* Predicted DLT rate = $\frac{\text{Predicted total number of patients who will experience DLT at the current dose}}{\text{Total number of patients treated at the current dose}}$

Abbreviations: DLT = dose-limiting toxicity; MTD = maximum tolerated dose.

5.1.2.2 BMS-986315 in Combination with Nivolumab Dose Escalation Design (Part 1B)

Approximately 36 participants are expected to be treated during the BMS-986315 Combination with Nivolumab Dose Escalation (Part 1B) of the study guided by TITE-BOIN for the primary objective. Additionally, up to approximately 80 participants are expected to be treated across 2 SCCHN PD cohorts in combination with nivolumab.

Based on preliminary safety, PK, and pharmacodynamic data from Part 1A, the starting dose of BMS-986315 in Part 1B may be higher than the starting dose from Part 1A. Each dose level in

Part 1B, including the starting dose, will only be opened after at least that dose and one higher dose level in Part 1A have demonstrated tolerability during the DLT observation period. Additional cohorts in Parts 1A and 1B may proceed in parallel and will be separated by at least 2 dose levels (the current and 1 higher cleared in Part 1A). Each participant will be administered IV doses of BMS-986315 (in doses based on Part 1A data) combined with 480 mg of nivolumab Q4W (once per cycle), for up to 26 cycles of study therapy (104 weeks) unless criteria for study drug discontinuation are met earlier (see [Section 8](#)).

The combination dose escalation phase (Part 1B) of the study will evaluate the safety and tolerability of BMS-986315, given in combination with nivolumab, based on DLTs, using a TITE-BOIN. During the combination dose escalation phase, approximately 3 participants will be treated at each dose level. However, to allow for any unforeseen discontinuations (such as disease progression) before the 4-week DLT period (28 days) is completed, an extra participant may be enrolled in each dose escalation cohort. Therefore, there may be a total of 4 participants (3 + 1) at the start of each cohort, provided that the fourth participant is able to start dosing within approximately 1 week of the third participant in the same dose escalation cohort. Cohort tolerability assessment and subsequent dose recommendation will occur when at least 3 evaluable participants within a cohort have completed a 4 week DLT period or have been sufficiently followed, based on the TITE-BOIN design, to make an escalation decision depending on the number of DLTs so far. Any toxicities that occur beyond the DLT period will be considered in making dose level decisions and/or dose level modifications. Additional information on DLTs can be found in [Section 5.1.3](#).

If the potential DLT occurring in the third-evaluable participant regarding any specific dose level does not influence the dose recommendation by TITE-BOIN, the next dose level may proceed without waiting for the third participant to complete the corresponding DLT-observation period, after discussion and agreement between the Sponsor and investigators. Continuous reassessment of dose recommendation, by TITE-BOIN in the BMS-986315 in Combination with Nivolumab Dose Escalation (Part 1B) will be carried out for each dose level. Planned dose levels for dose escalation are provided in [Section 5.1](#).

Planned dose levels may be modified based upon the DLT data in the evaluated doses and clinical evaluation of all available safety and PK/pharmacodynamic data. Once the tolerability (during the DLT evaluation) of a dose level has been established, additional participants may be added at that dose level to better characterize the safety, PK, and pharmacodynamic profiles.

5.1.2.3 BMS-986315 in Combination with Cetuximab Dose Escalation Design (Part 1C)

Approximately 36 participants are expected to be treated during the BMS-986315 combination with cetuximab dose escalation (Part 1C) of the study guided by TITE-BOIN for the primary objective. Additionally, up to approximately 80 participants are expected to be treated in the SCCHN PD cohorts in combination with cetuximab.

Based on preliminary safety, PK, and pharmacodynamic data from Part 1A, the starting dose of BMS 986315 in Part 1C may be higher than the starting dose from Part 1A. Each dose level in Part

1C, including the starting dose, will only be opened after at least that dose and 1 higher dose level in Part 1A have demonstrated tolerability during the DLT observation period. Additional cohorts in Parts 1A and 1C may proceed in parallel and will be separated by at least 2 dose levels (as indicated above). Each participant will be administered Q4W IV doses of BMS-986315 (in doses based on Part 1A data) combined with 500mg/m² of cetuximab Q2W for up to 26 cycles of study therapy (104 weeks) unless criteria for study drug discontinuation are met earlier (see [Section 8](#)).

The combination dose escalation phase (Part 1C) of the study will evaluate the safety and tolerability of BMS-986315, given in combination with cetuximab, based on DLTs, using a TITE-BOIN. During the combination dose escalation phase, approximately 3 participants will be treated at each dose level. However, to allow for any unforeseen discontinuations (such as disease progression) before the 4 week DLT period (28 days) is completed, an extra participant may be enrolled in each dose escalation cohort. Therefore, there may be a total of 4 participants (3 + 1) at the start of each cohort, provided that the fourth participant is able to start dosing within approximately 1 week of the third participant in the same dose escalation cohort. Cohort tolerability assessment and subsequent dose recommendation will occur when at least 3 evaluable participants within a cohort have completed a 4 week DLT period or have been sufficiently followed, based on the TITE-BOIN design to make an escalation decision depending on the number of DLTs so far. Any toxicities that occur beyond the DLT period will be considered in making dose level decisions and/or dose level modifications. Additional information on DLTs can be found in [Section 5.1.3](#).

If the potential DLT occurring in the third-evaluable participant regarding any specific dose level does not influence the dose recommendation by TITE-BOIN, the next dose level may proceed without waiting for the third participant to complete the corresponding DLT-observation period, after discussion and agreement between the Sponsor and investigators. Continuous reassessment of dose recommendation, by TITE-BOIN in the BMS-986315 in combination with cetuximab dose escalation (Part 1C) will be carried out for each dose level. Planned dose levels for dose escalation are provided in [Section 5.1](#).

Planned dose levels may be modified based upon the DLT data in the evaluated doses and clinical evaluation of all available safety and PK/pharmacodynamic data. Once the tolerability (during the DLT evaluation) of a dose level has been established, additional participants may be added at that dose level to better characterize the safety, PK, and pharmacodynamic profiles.

5.1.2.4 Pharmacodynamic Cohorts

As introduced in previous sections, PD cohorts are included in Part 1A (1 cohort) and Parts 1B and 1C (up to 2 cohorts) at different dose levels. Each of these PD cohorts will only be open once the dose level has been demonstrated to be tolerated. The objective of the PD cohorts is to obtain pharmacodynamic information, and additional data on safety, tolerability, preliminary efficacy, and PK, in participants with SCCHN. The goal of each PD cohort is to obtain approximately 10 paired biopsy samples of participants who are considered as “biomarker negative” and 20 paired biopsy samples of participants who are considered as “biomarker positive” which is consistent with the expected natural prevalence of these biomarkers in SCCHN. Therefore, up to

approximately 40 participants are expected to be treated in each PD cohort in order to have 30 evaluable participants (with paired biopsies). A fresh screening tumor biopsy will be assessed for CD8 and total HLA-E using CLIA validated IHC assays. [REDACTED]

[REDACTED]
[REDACTED]
[REDACTED]. All PD cohorts will enroll participants with SCCHN. Participants treated in the PD cohorts will be administered IV doses of BMS-986315 according to the dose defined for the PD cohort (e.g., 1200 mg or 2400 mg) Q4W once per cycle, for up to 26 cycles (104 weeks) of study therapy, unless criteria for study drug discontinuation are met earlier (see [Section 8.1](#)). In Part 1B, BMS-986315 will be combined with nivolumab 480mg Q4W. In Part 1C, BMS-986315 will be combined with cetuximab 500 mg/m² Q2W.

5.1.3 Dose Limiting Toxicities

For the purpose of guiding decisions regarding dose escalation in Parts 1A, 1B, and 1C, DLTs will be defined based on the incidence, intensity, and duration of AEs excluding toxicities clearly related to disease progression or intercurrent illness. The DLT period will start on the first day of cycle 1 and end at day 28 (therefore, 4 weeks) in Parts 1A, 1B and 1C. The severity of AEs will be graded according to National Cancer Institute (NCI) Common Terminology Criteria for Adverse Events (CTCAE) v5.0.

For the purpose of participant management, DLTs that occur at any time during treatment (not limited to DLT observation period) will result in study drug being held pending evaluation of the event being related to study drug, in accordance with [Section 7.4](#). A participant is considered DLT evaluable if receiving 1 dose of BMS-986315 in Part 1A, 1 dose of BMS-986315 and nivolumab (480mg) in Part 1B, or 1 dose of BMS-986315 and cetuximab (500 mg/m²) in Part 1C, and completing the DLT observation period.

Participants who withdraw from the study during the 4 week DLT evaluation period for reasons other than a DLT may be replaced with a new participant at the same dose level. The incidence of DLT(s) during the 4 week DLT evaluation period will be used in dose escalation decisions and to define the MTD/RP2D in monotherapy and in combination with nivolumab or cetuximab. AEs occurring after the 4-week DLT period will be considered for the purposes of defining the RP2D upon agreement between the Sponsor and Investigators. Participants experiencing a DLT will not be retreated with study drug (except for Grade 3 or 4 acneiform rash in Part 1C), and will enter the safety follow-up period of the study.

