Procedure ^a	Cycle 1 (28 days)				Cycle 2 (28 days)				Cycle 3 and Beyond (28 days)				EOT ^b	Notes
	D1	D8 ^c	D15 ^c	D22 ^c	D1 ^c	D8 ^c	D15 ^c	D22 ^c	D1 ^c	D8 ^c	D15 ^c	D22 ^c		
Biomarker Assessments														
Tumor Biopsy ^e	See Section 9.8 and Table 9.8-1												On treatment biopsy should be performed on C1D22 (plus or minus 5 days)	
Blood, Serum, and Plasma Pharmacodynamic Sampling, and SARS-CoV-2 Serology	See Section 9.8 and Table 9.8-1												SARS-CoV-2 serum will be collected predose at C1D1 and collected approximately every 6 months during study treatment to be used for potential future measurements of anti-SARS-CoV-2 serology (anti-SARS-CoV-2 total or IgG). SARS-CoV-2 serum should also be collected approximately 4 weeks after a documented or suspected anti-SARS-CoV-2 infection.	
Imaging Assessments^f														
Body Imaging	See Notes												Contrast enhanced CT of the chest, CT/MRI of the neck (required for SCCHN participants), abdomen, pelvis, and all other known and/or suspected sites of disease will occur every 8 weeks starting 8 weeks from date of first dose (\pm 7 days) until disease progression and treatment discontinuation, whichever occurs	

Table 2-2: On Treatment Procedural Outline (CA047004)

Procedure ^a	Cycle 1 (28 days)				Cycle 2 (28 days)				Cycle 3 and Beyond (28 days)				EOT ^b	Notes
	D1	D8 ^c	D15 ^c	D22 ^c	D1 ^c	D8 ^c	D15 ^c	D22 ^c	D1 ^c	D8 ^c	D15 ^c	D22 ^c		
														later. See Section 9.1.1.1 for further details.
Brain Imaging														Participants with a history of brain metastasis or symptoms should have a surveillance MRI study per standard of care (approximately every 12 weeks), or sooner if clinically indicated. CT of the brain without and with contrast can be performed if MRI is contraindicated. See Section 9.1.1.1 for further details
Study Treatment														
BMS-986315 Administration (Part 1A, 1B and Part 1C)	X				X				X					If a dose is delayed, the procedures scheduled for that same timepoint should also be delayed to coincide with when that timepoint's dosing actually occurs.
Nivolumab Administration (Part 1B only)	X				X				X					
Cetuximab Administration (Part 1C only)	X		X		X		X		X		X			

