The dose escalation of BMS-986315 in combination with cetuximab (Part 1C) will evaluate the safety and tolerability of escalating doses of BMS-986315 in combination with cetuximab, to determine the combination MTD/RP2D in SCCHN participants. Treatment in Part 1C will be initiated in a staggered manner relative to the BMS-986315 Monotherapy Escalation (Part 1A). Specifically, Part 1C can be initiated upon the decision to escalate when at least 2 BMS-986315 dose levels (the current and 1 higher) in Part 1A have been cleared for safety in accordance with dose escalation rules, after which, dose escalation in Part 1A and Part 1C will proceed in parallel separated by 2 dose levels as indicated above, (see [Section 7.2](#)). At no point will the dose of BMS-986315 administered in combination with cetuximab in Part 1C exceed the highest dose determined to be tolerated in Part 1A. In Part 1C, the dose of BMS-986315 will be escalated, whereas the dose of cetuximab will be fixed at 500mg/m² Q2W. However, if it appears that a planned dose level is associated with an unacceptable frequency of toxicities, then intermediate dose levels, alternative BMS-986315 administration schedules, or de-escalating doses of cetuximab may be evaluated. Specifically, if toxicity attributable solely to cetuximab is found to be in excess as compared to the known toxicity profile of the label dose of 400mg/m² followed by 250mg/m² QW, then a decision may be made to change the cetuximab dosing regimen for all of Part 1C.

The safety and tolerability of BMS-986315 in combination with cetuximab will be evaluated using TITE-BOIN design also used to guide escalation decisions. Additional cohorts of participants will be enrolled in up to 2 dose levels previously cleared for safety. The BMS-986315 in combination with cetuximab PD cohorts, will be implemented in order to gather additional information on pharmacodynamic activity, safety, tolerability, preliminary efficacy and PK in SCCHN participants treated with BMS-986315 in combination with cetuximab. Please refer to [Section 5.1.2.4](#) for additional information on the PD cohorts.

The study consists of 4 periods: Screening, Treatment, Safety Follow-up, and Survival Follow-up (up to 2 years following the EOT of study drug). The duration of the study will be approximately 4 years. The study design schematic is presented in [Figure 5.1-1](#). A detailed schematic for study period and participant flow is presented in [Figure 5.1-2](#).

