7.4.1 Dose Delays Due to Toxicity

Participants who experience the following must have all study drug(s) withheld:

- Potential DLTs, until DLT relatedness is defined.
- Select AEs and laboratory abnormalities:
 - \geq Grade 1 pneumonitis
 - \geq Grade 2 abnormality in AST, ALT or total bilirubin
 - \geq Grade 2 creatinine increased
 - \geq Grade 2 diarrhea or colitis
 - \geq Grade 2 neurological AE
 - Grade 2 myocarditis
 - AE, laboratory abnormality, or concurrent illness that, in the judgment of the Investigator, warrants delaying study drug administration.
 - For SCCHN participants in Part 1C: Grade 3 or 4 acneiform rash
 - Confirmed SARS-CoV-2 infection

Criteria for participants who are required to permanently discontinue both study drugs is listed in [Section 8](#). Participants not meeting guidelines for permanent discontinuation will be permitted to

resume therapy based on the criteria specified below in [Section 7.4.2](#). Participants eligible to resume study therapy will resume study therapy at the nominal treatment visit following their last received study medication dose.

The end of cycle tumor assessments, such as computed tomography (CT), magnetic resonance imaging (MRI), or positron emission tomography (PET), will continue on a Q8W schedule relative to the participant's first dose, regardless of any treatment delay incurred

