15	5	1		>0.28	≤ 0.28
15	5	2		>1.35	≤ 1.35
15	5	3		>2.42	≤ 2.42
15	5	4		>3.5	≤ 3.5
15	5	5		>4.57	≤ 4.57
15	5	6		>5.64	≤ 5.64
15	5	7		>6.72	≤ 6.72
15	5	≥ 8	Suspend	Suspend	Suspend
15	6, 7	≤ 9			Y
15	≥ 8	≤ 7			Y&Elim

Note: "No. Patients Treated" is the total number of patients treated at the current dose level, "No. DLTs observed" is the number of patients who experienced DLT at the current dose level, "No. Pending patients" denotes the number of patients whose DLT data are pending at the current dose level, "STFT" is the standardized total follow-up time for the patients with data pending. "Y" represents "Yes", and "Y&Elim" represents "Yes and Eliminate". When a dose is eliminated, all higher doses should also be eliminated.

After the trial is completed, select the MTD based on isotonic regression as specified in Yuan et al. (2018). This computation is implemented by the "Estimate MTD" tab of the BOIN Design Desktop Program (Venier et al., 2018). Specifically, select as the MTD the dose for which the isotonic estimate of the toxicity rate is closest to the target toxicity rate. If there are ties, select the higher dose level when the isotonic estimate is lower than the target toxicity rate and select the lower dose level when the isotonic estimate is greater than or equal to the target toxicity rate.

Operating characteristics

Table 2 shows the operating characteristics of the trial design based on 1000 simulations of the trial using the BOIN Design Desktop Program (Venier et al., 2018). The time to toxicity is simulated from a uniform distribution $\text{Unif}(0, T)$, and the patient accrual follows a Poisson process at the rate of 3 patients per month. The operating characteristics show that the design selects the true MTD, if any, with high probability and allocates more patients to the dose levels with the DLT rate closest to the target of 0.3.

Table 2: Operating Characteristics of the TITE-BOIN design.

	Dose Level					Number of Patients	% Early Stopping	Duration (months)
	1	2	3	4	5			
Scenario 1								
True DLT Rate	0.30	0.47	0.53	0.58	0.64			
Selection %	64.7	16.8	2.6	0.5	0.0		15.4	10.3
# Pts Treated	11.4	5.8	2.4	0.9	0.3	20.84		
Scenario 2								
True DLT Rate	0.01	0.11	0.30	0.45	0.67			
Selection %	0.5	21.1	59.7	18.4	0.3		0.0	12.4
# Pts Treated	1.8	7.0	10.9	6.3	1.8	27.84		
Scenario 3								
True DLT Rate	0.02	0.07	0.13	0.30	0.47			
Selection %	0.1	2.0	24.6	57.7	15.6		0.0	12.9
# Pts Treated	1.5	2.5	7.1	10.8	5.9	27.84		
Scenario 4								

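### Part 1C counts a participant as DLT-evaluable after one of the two cetuximab doses scheduled in the 28-day window

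*Combined protocol and SAP*

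**What the plan says.** **Window and schedule.** Section 5.1.3 sets the DLT window: "The DLT period will start on the first day of cycle 1 and end at day 28". Section 5.1 describes Part 1C as escalating BMS-986315, "whereas the dose of cetuximab will be fixed at 500mg/m² Q2W". The row of Table 2-2 that begins "Cetuximab Administration (Part 1C only" marks Day 1 and Day 15 of Cycle 1.

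**Evaluability.** Section 5.1.3 asks for "1 dose of BMS-986315 and cetuximab (500 mg/m²) in Part 1C, and completing the DLT observation period". The Part 1B rule has the same form with nivolumab 480 mg, which is given once per 28-day cycle.

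**Replacement.** Section 5.1.3 says: "Participants who withdraw from the study during the 4 week DLT evaluation period for reasons other than a DLT may be replaced". Section 7.2 also deals only with participants discontinued from the study. Neither mentions a missed or late cetuximab dose.

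**Counting.** The note to Table 1 in Appendix 8 says that the number treated "is the total number of patients treated at the current dose level". It makes no reference to cetuximab received. Table 10.2-1 defines no DLT-evaluable population.

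**Change of partner regimen.** If toxicity due solely to cetuximab is excessive, Section 5.1 says "then a decision may be made to change the cetuximab dosing regimen for all of Part 1C". Section 5.5.3 allows a change for the entire program at any time, and Section 5.1 allows lower nivolumab doses in Part 1B.

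**The concern.** The evaluability rule suits a partner drug given once per window. Applied to a drug given twice in the window, it accepts half the planned dose. A participant who had Day 1 cetuximab, missed Day 15 and reached Day 28 without a DLT is complete, not pending, and is not replaced. Table 1 then weighs that participant the same as one who tolerated both infusions.

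The DLT incidence in this window guides escalation and defines the combination MTD/RP2D (Section 5.1.3). If the second infusion adds any DLT risk, such participants pull the observed rate down and make escalation slightly more likely at a dose that is too toxic. Some of the holds that delay Day 15 are themselves for toxicity, so the under-dosed participants need not be a random subset.

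**Working it through.** **1. Reproduce the plan's boundaries.** Section 10.1.1 gives a target of 30%, escalation at 23.6% and de-escalation at 35.9%. The documents do not state the BOIN alternatives, so the usual φ₁ = 0.6φ = 0.18 and φ₂ = 1.4φ = 0.42 are assumed.

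- λₑ = ln(0.82/0.70) / ln[(0.30 × 0.82)/(0.18 × 0.70)] = 0.2365
- λ_d = ln(0.70/0.58) / ln[(0.42 × 0.70)/(0.30 × 0.58)] = 0.3585

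Both agree with the plan. With 3 treated and none pending, 0 DLTs means escalate, 1 means stay and 2 means de-escalate, as in Table 1.

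**2. Planned cetuximab in the window.** Doses fall on Days 1 and 15, so 2 × 500 = 1000 mg/m². The evaluability rule is met at 500 mg/m², which is 50%.

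**3. Can Day 15 be lost without a DLT?** Yes.

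- Section 7.4.1 states: "Participants who experience the following must have all study drug(s) withheld". Its list includes events below Grade 3, such as Grade 1 pneumonitis and Grade 2 diarrhea, creatinine or transaminase changes.
- A Grade 3 rash that improves is not a DLT (Sections 5.1.3.3 and 5.1.3.5), but Section 7.4.2.1 delays the infusion by 1 to 2 weeks. Counted from Day 15, that is Day 22 to Day 29.
- Section 7.4.2 requires at least 10 days after a SARS-CoV-2 infection, or 20 if severe. From Day 15 that is Day 25 or Day 35, so mainly a severe or late infection pushes the dose out of the window.
- A visit may simply be missed.

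**4. Size.** Assumptions not in the documents: each participant misses Day 15 with probability m = 10% to 20%; the true DLT rate on both doses is p = 40%; a share f of the cumulative hazard does not depend on the second dose. A one-dose participant is then DLT-free with probability (1 − p)^f, and

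P(0 of 3) = [(1 − m)(1 − p) + m(1 − p)^f]³.

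With nobody under-dosed it is 0.6³ = 21.6%. For f = 0.5, (0.6)^0.5 = 0.7746:

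- m = 10%: (0.9 × 0.6 + 0.1 × 0.7746)³ = 0.6175³ = 23.5%
- m = 20%: (0.8 × 0.6 + 0.2 × 0.7746)³ = 0.6349³ = 25.6%

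The apparent DLT rate falls from 40% to 1 − 0.6175 = 38.3% and 1 − 0.6349 = 36.5%.

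Other values of f, by the same formula at p = 40%:

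| f | (0.6)^f | m = 10% | m = 20% |
|---|---|---|---|
| 0.50 | 0.7746 | 23.5% | 25.6% |
| 0.75 | 0.6817 | 22.5% | 23.4% |
| 0.90 | 0.6315 | 21.9% | 22.3% |

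At p = 50% and f = 0.5, where (0.5)^0.5 = 0.7071, P(0 of 3) is (0.45 + 0.0707)³ = 14.1% to (0.40 + 0.1414)³ = 15.9%, against 12.5%.

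Given that exactly one of three participants is under-dosed (p = 40%, f = 0.5), it is 0.6² × 0.7746 = 27.9%. At these miss rates a cohort of three contains at least one such participant with probability 1 − 0.9³ = 27% to 1 − 0.8³ = 49%.

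**The case against.** **The effect is small and partly mitigated.** Section 7.4.2.3 puts about 90% of severe cetuximab infusion reactions at the first infusion, so the half-hazard split is generous. With the 112-hour half-life in Section 3.2.3.1 and simple linear kinetics (an assumption), 14 days is 336/112 = 3 half-lives. About 12.5% of the first dose remains at Day 15, and the first peak is about 87.5% of the steady-state peak. Most Grade 3 or higher events that would stop cetuximab are already DLTs. Table 2-2 treats a delayed dose as moved rather than skipped. Section 5.1.2.3 considers later toxicity, Section 10.1.1 bases the final dose on all available data, and each Part 1C level opens only after that dose and one higher are tolerated in Part 1A. All of this stands and limits the size. None of it decides who counts as a completed DLT-free observation.

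**Stronger readings the documents do not support.** A reader might infer that Part 1C ignores cetuximab exposure altogether. It does not: on the natural reading, one 500 mg/m² dose is required.

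A reader might also infer that DLT counts carry over when the cetuximab regimen is changed. The documents are silent. Pooling is what Appendix 8 would give if applied unchanged, yet Section 5.1.3 read literally would make nobody starting on another regimen evaluable. The change is contingent, and Table 2-2 has no weekly cetuximab visits, so a move to the weekly regimen would itself need a revised schedule. Restarting the counts is not clearly better: it discards DLTs due to BMS-986315, could reopen an eliminated level and uses up the 36-participant maximum.

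**Conclusion.** The point holds for the evaluability rule. As written, Section 5.1.3 accepts half the planned cetuximab in the DLT window and provides no replacement, so an under-dosed, DLT-free participant counts in full. The direction is towards under-stating the combination DLT rate, provided that the second dose carries some risk.

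The size is modest: at a true rate of 40%, the chance of escalating on 0 of 3 rises by about 2 to 4 percentage points (21.6% to 23.5–25.6%) under the half-hazard split. The rise is below 1 point if 90% of the hazard does not depend on the second dose. The miss rate and the hazard split are assumptions.

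Secondarily, Section 5.1.3 names fixed partner doses while Sections 5.1 and 5.5.3 allow the partner regimens to change, and nothing says how earlier DLT counts would be treated. That is an inconsistency to reconcile, not evidence that counts are pooled across regimens.

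**What to change.** In Section 5.1.3, define a Part 1C participant as DLT-evaluable if they have a DLT in the window, or if they complete the window having received BMS-986315 and every cetuximab dose scheduled in it. Extend the replacement rule to DLT-free participants who miss the Day 15 dose for reasons unrelated to treatment. Flag those who miss it for treatment-related toxicity at the dose decision, so that they are not read as plain DLT-free observations. The note to Table 1 should say how its counts relate to this definition.

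Separately, reconcile the fixed 500 mg/m² and 480 mg in Section 5.1.3 with the permitted regimen changes in Sections 5.1 and 5.5.3, and state how DLT counts collected before a change are handled. No particular regimen or reset rule is proposed here.

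The cost is wording plus an occasional replaced participant within the 36-participant maximum. At the assumed miss rates, 3 × 0.10 = 0.3 to 3 × 0.20 = 0.6 participants per cohort of three would miss the dose, and only those who miss it for unrelated reasons are replaced. The optional fourth participant in Section 5.1.2.3 can absorb some of this.
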